3.2.2. ANNUALIZED INFUSION RATE (AIR)

AIR following SPK-8016 administration and beginning 28 days following SPK-8016 administration will be listed by participant. Two main types of infusions were reported: “all infusions” and “infusions to treat bleeds”. The number of recorded FVIII infusion events will be categorized and analyzed using these two main categories of infusions. The reported infusions during the prior 52-week hemophilia history were “all infusions” only.

AIR Calculation Rules:

Censoring Rule: If a participant loses transgene derived FVIII, the duration of follow-up time for calculation of AIR will be censored on the day in which the central lab one-stage FVIII activity level falls to equal or below diagnostic historical value 28 days or later following SPK-8016 infusion.

AIR Calculation Formula:

AIR post 28 days will be calculated as follows:

$$AIR_{28} = \frac{365.25 * \text{observed number of FVIII infusions}}{EFF\ FUP\ (in\ days) - 28}$$

rounded to the nearest integer.

AIR post day0 will be calculated as follows:

$$AIR = \frac{365.25 * \text{observed number of FVIII infusions}}{EFF\ FUP\ (in\ days)}$$

rounded to the nearest integer. EFF FUP, the duration of efficacy follow-up.

Change in AIR and AIR28 will only be calculated for the number of recorded “all infusions” because only all infusions are collected for the prior to gene therapy period.

Change in AIR will be calculated as:

$$\text{Change in AIR} = \text{Post Infusion AIR} - \text{Baseline AIR}$$

Change in AIR28 will be calculated as:

$$\text{Change in AIR28} = \text{Post Infusion AIR28} - \text{Baseline AIR}$$

3.3. PHARMACOKINETICS ANALYSIS

FVIII:C activity level (one stage; central lab-recorded) following SPK-8016 administration will be listed by participant.

3.3.1. PEAK FVIII ACTIVITY

The peak FVIII:C activity level and the time to the peak will be computed for each participant.

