The infusion of SPK-8016 to the first 2 participants at each dose level will be staggered by at least 6 weeks to mitigate acute safety risk. Additionally, at least 6 weeks of follow up data from up to 4 participants in a given dose level will undergo review by the DMC prior to infusing the first participant in the next dose level.

Pharmacokinetic Evaluation:

The responses to SPK-8016 will consist of peak and steady-state values of circulating vector-derived FVIII activity levels after SPK-8016 infusion. Additional pharmacokinetic (PK) evaluation of SPK-8016 is carried out by analysis of serum urine, semen, saliva for the presence of vector DNA.

Efficacy Evaluation:

The following information will be collected for efficacy evaluations:

- Vector-derived factor VIII in circulation (FVIII:C) activity levels (including additional peak and steady-state levels)
- FVIII antigen level
- Number of FVIII infusions (prophylaxis and/or on-demand)
 - Number of bleeding episodes (spontaneous and traumatic)
 - Annualized FVIII usage (AFU)
 - Annualized bleeding rate (ABR) (spontaneous and traumatic)
- Joint assessments
- Activities assessments
- Quality-of-life assessments
- Health-economic assessments

**Investigational
Product
Description:**

[Redacted text block]

[REDACTED]

**Dose Expansion/
Escalation Plan:**

Each dose level is planned to enroll and dose a minimum of 2 participants. The first 2 participants at each dose level will be dosed at least 6 weeks apart to ensure the safety and tolerability of the vector administration.

Dose-Level and Cohort Expansion:

- A. ***Dose-Level Expansion*** - After 2 participants are dosed at a given dose-level, it may be possible to expand that cohort to up to 10 participants if there is evidence of FVIII:C increases above 5% of normal in either participant by Week 4 post-vector administration. This initial expansion will provide additional information about the variability of responses within the same dose-level.
- B. ***New Cohort Expansion*** – For Cohorts 1 and 2 of the 5×10^{11} vg/kg dose, the first 2 participants in each cohort will be infused at least 6 weeks apart. After 2 participants are dosed in a cohort, an initial expansion of up to 3 participants may occur and, thereafter, an additional expansion for up to a total of 10 participants may occur. The additional expansion may occur in 1 or more cohorts.

Dose Escalation:

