4.1.6 Dosing Period (Days 0, 1)

Assessments and procedures to be performed on Dosing Day (Day 0) are described in [Table 1](#). All participants will administer a prophylactic infusion of 50 IU/kg of their current FVIII concentrate the morning of Day 0. This may be self-administered and recorded in the subject infusion log. Site assistance is permitted for the FVIII infusion. On Day 0, participants in Cohort 2 will receive a dose of [REDACTED] intravenously over 60 minutes, with the [REDACTED] infusion to be completed at least 4 hours (up to 24 hours) prior to the start of vector administration. The [REDACTED] dose will not exceed [REDACTED] (Please see [REDACTED] prescribing information [[Genentech, 2019](#)]). Participants will receive a single IV infusion of SPK-8016 at the vector-administration center. The complete dose of SPK-8016 will be infused via infusion pump over approximately 60 minutes. Vital signs will be taken at various time-points from the start of infusion (see [Table 1](#)).

Blood samples for immune profiling will be collected pre-administration of [REDACTED] (3-7 Days Prior), and SPK-8016, and 30 (± 2) minutes, 2 hours (± 10 minutes), 5 hours (± 10 minutes), and 24 (± 1) hours from the completion of the SPK-8016 infusion. PAX Gene will be collected pre-administration of [REDACTED], pre-administration of SPK-8016, and 5 hours (± 10 minutes) and 24 (± 1) hours from the completion of the SPK-8016 infusion. Additional blood samples, including FVIII activity levels, will also be collected pre-infusion of SPK-8016.

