10.3 Populations for Analyses

The Full Analysis Set (FAS) is defined as all participants who receive the infusion of SPK-8016. The analyses of efficacy will be performed in this population, including the evaluation of vector-derived FVIII:C activity for estimation of peak and steady-state activity levels. As this is an open-label study, additional subgroup analyses may be specified following clinical review.

The Safety Population will include all participants who receive any study-mandated medication and will be used to summarize all safety data.

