1.2.2. PHARMACOKINETICS ENDPOINTS

- Peak FVIII activity
- Median FVIII activity from weeks 40 through 52 post-SPK-8016 infusion

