3.7.2. DAYS TO ONSET OF EVENTS

For efficacy assessments, including bleeding events, FVIII:C activity levels and other laboratory data, and safety assessments of adverse events and concomitant medications/procedures days of follow-up and days to onset of the event/medication/procedure from administration of SPK-8016 will be calculated as:

$$\text{Days to onset of events} = (\text{study visit or assessment date}) - (\text{SPK-8016 infusion date}).$$

This preserves the protocol-specified nomenclature for a Day 0 record on the study data base.

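### SAP 3.3.1 sets no washout for infused FVIII, so in a low expressor the reported peak and time to peak can be residual concentrate from the Day 0 dose of 50 IU/kg

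*SAP*

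**What the plan says.** SAP 1.2.2 names two pharmacokinetic endpoints, one of which is "Peak FVIII activity". The data are described in SAP 3.3: "FVIII:C activity level (one stage; central lab-recorded) following SPK-8016 administration will be listed by participant". The derivation in SAP 3.3.1 is a single sentence: "The peak FVIII:C activity level and the time to the peak will be computed for each participant". It gives no first eligible day and no rule for samples taken after infused FVIII. The same peak is listed again among the coagulation parameters in SAP 3.4.3.

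The protocol has a narrower quantity in mind. Its summary speaks of "peak and steady-state values of circulating vector-derived FVIII activity levels after SPK-8016 infusion", and section 10.3 of "vector-derived FVIII:C activity for estimation of peak and steady-state activity levels". Peak activity is also part of a primary endpoint in protocol 3.3.

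On the dosing day, protocol 4.1.6 states: "All participants will administer a prophylactic infusion of 50 IU/kg of their current FVIII concentrate the morning of Day 0". In Cohort 2 the concentrate is given before the pre-treatment (Table 1 note 16; section 7.4), with the pre-treatment "infusion to be completed at least 4 hours (up to 24 hours) prior to the start of vector administration". Central FVIII activity is measured on Day 1 (6.7.4) and at each visit from Day 3, with a window of ±2 days (6.8.1). Section 7.9.2 also permits FVIII for bleeds, and prophylaxis in the first 14 days if the investigator judges it necessary.

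**The concern.** A one-stage assay result does not separate concentrate from transgene product. The schedule places the first post-vector samples while the Day 0 dose is still decaying. Appendix 4 gives early bleed protection, lasting part of the first week, as a reason for that infusion, so circulating concentrate is expected then.

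No other rule closes the gap. The protocol's condition on exogenous FVIII (3.3, 10.5.2) is attached to steady state only. It also counts from vector administration, so it would not catch a dose given before the vector. The one caution about peak, in protocol 10.5.3, concerns corticosteroids. The SAP does offer bleeding and infusion rates that start at Day 28, and it looks for loss of expression only from Day 28. Peak has no comparable guard.

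At stake is one of the SAP's two pharmacokinetic endpoints. In an affected participant the table would show concentrate as the gene therapy's peak. SAP 3.7.2 counts days as assessment date minus infusion date, so it would also show a time to peak of 1 or 3 days.

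**Working it through.** The plan gives no figure for residual FVIII, so there is none to reproduce. The check is first-order decay of the Day 0 dose.

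**Inputs from the documents**
- Dose 50 IU/kg (protocol 4.1.6).
- Product half-life 10.8 to 19.7 h (protocol 2.3.2).
- Vector infusion about 1 h; Cohort 2 pre-treatment 1 h, finished 4 to 24 h before vector (4.1.6).

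**Assumptions, not in the documents**
- Incremental recovery 2 IU/dL per IU/kg, range 1.5 to 2.5.
- 1 to 7 h from FVIII to the start of vector; in Cohort 2, 0 to 4 h from FVIII to pre-treatment.
- Day 1 sample 24 h after the end of the vector infusion.

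**Formula.** Starting level C0 = 50 × recovery = 100% of normal (75-125% over the range). Residual = C0 × 2^(−t / half-life).

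**Elapsed time**
- Day 1, outside Cohort 2: (1 to 7) + 1 + 24 = 26 to 32 h.
- Day 1, Cohort 2: (0 to 4) + 1 + (4 to 24) + 1 + 24 = 30 to 54 h.
- Nominal Day 3 adds 48 h: 74 to 80 h, and 78 to 102 h in Cohort 2.

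**Results.** The low end pairs the longest gap with 10.8 h; the high end pairs the shortest gap with 19.7 h. For Day 1 outside Cohort 2 these are 100 × 2^(−32/10.8) = 12.8% and 100 × 2^(−26/19.7) = 40.1%.

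| Sample | Hours after FVIII | Recovery 2 | Recovery 1.5-2.5 |
|---|---|---|---|
| Day 1 | 26-32 | 12.8-40.1% | 9.6-50.1% |
| Day 1, Cohort 2 | 30-54 | 3.1-34.8% | 2.3-43.5% |
| Day 3 | 74-80 | 0.59-7.4% | 0.44-9.3% |
| Day 3, Cohort 2 | 78-102 | 0.14-6.4% | 0.11-8.0% |

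The visit window widens this. Outside Cohort 2 at recovery 2, a Day 3 visit held on Day 2 (50-56 h) gives 2.7-17.2%, and one held on Day 5 (122-128 h) gives 0.03-1.4%. By 168 h the residual is at most 0.34% anywhere in the range.

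**Scale.** Protocol 2.1.3.2 cites about 12% as possibly enough to protect against spontaneous joint bleeds. At recovery 2 the residual stays above 12% for half-life × log2(100/12) = 33.0 to 60.3 h.

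**Washout length.** Time to fall below 1% is half-life × log2(C0): 71.8 to 130.9 h at recovery 2, and 67.3 to 137.2 h (2.8 to 5.7 days) over the range. With a 19.7 h half-life, five days leaves 1.47% (1.83% at recovery 2.5). Six days leaves 0.63% (0.79%), or 0.97% at recovery 2.5 if 50 IU/kg had been repeated every 48 h.

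**Week 40-52 median (SAP 3.3.2).** This has no washout either, but it is sturdier. Of the three scheduled values (weeks 40, 46 and 52), one contaminated value cannot lift the median above the larger of the two clean ones; that takes two. Participants still on immunomodulation may have weekly values as well (protocol 6.8.2).

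**The case against.** The effect is conditional. Residual concentrate becomes the peak only if the true peak is lower, and the documents report no peaks. Protocol 2.5 gives levels around 6% in three of the first four participants and above 20% in the fourth, but these are achieved levels. Three of the four received prednisone from week 3-6 (4.1.3), and protocol 10.5.3 expects corticosteroids to raise expression, so their peaks may have been well above 6%. Their Day 0 FVIII dose is not stated. This stands: those levels cannot be used to count affected participants.

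The consequence is also bounded. The study tests no hypothesis, every value is listed by participant so a Day 1 peak could be noticed, and dose decisions rest on Week 4, Week 6 or later activity. That limits the harm but does not correct the endpoint. A reader who suspects a Day 1 peak still has no pre-stated rule for replacing it, and in an open-label study that choice should not be made after seeing the data.

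Finally, the 1% threshold and six-day default are matters of judgement. Protocol 6.4.1 accepts historical or sparse-sample PK and does not say that the parameters reach the analysis database. Both points are fair. They argue for treating the threshold and default as examples and for having a simple fallback, not for leaving the rule out.

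**Conclusion.** The concern holds. Followed as written, SAP 3.3.1 returns infused product as the peak in any participant whose true peak lies below the residual level at a sampled visit. On Day 1 that level is about 13-40% of normal outside Cohort 2 and 3-35% in Cohort 2 at recovery 2; at nominal Day 3 it is at most about 7%. These sizes rest on the assumed recovery and lead times and on simple exponential decay. Outside Cohort 2 the Day 1 residual is still 9.6% at the lowest recovery considered, with the shortest half-life and longest gap. Prophylaxis to Day 14 or treatment of a bleed can contaminate later samples in the same way. The Day 0 sample is drawn before SPK-8016 (Table 1 note 17) and is not a source. How many participants are affected cannot be stated from the documents. This is a defect in one derived endpoint of a descriptive study, and it should be corrected in the SAP.

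**What to change.** In SAP 3.3.1, and for the peak listed in 3.4.3, exclude from peak and time to peak any FVIII:C sample drawn within a pre-stated washout after any recorded FVIII infusion, counting the Day 0 dose. One workable rule is to exclude until the participant's own PK profile predicts a residual below 1%, with a fixed default such as six days where that profile is unusable. List the excluded samples. If none remains, keep the participant in the table, labelled as on FVIII, with the unrestricted value shown.

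For the week 40-52 median, exclude nothing. Flag samples within the washout, show the median with and without them as a sensitivity analysis, and keep participants who resumed FVIII visible as such. Optionally, state in protocol 10.5.3 that the exogenous-FVIII condition in 10.5.2 governs the averages defined there. No change to any FVIII treatment is proposed.

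The cost is SAP wording and some derivation work; infusions are already logged. Day 1 is lost for everyone. Day 3 is lost for all under the six-day default. Under individual PK at recovery 2, a nominal Day 3 value outside Cohort 2 survives only for half-lives up to about 11-12 h (74/log2(100) = 11.1; 80/log2(100) = 12.0). With prophylaxis to Day 14 the default removes nominal Days 1, 3, 7, 10, 14 and 17: 6 of the 24 scheduled samples through Day 84 (Day 1 plus 23 visits). An early true peak could therefore be missed, and reported peaks may be lower. The median sensitivity analysis loses no data.

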3.3.2. MEDIAN FVIII ACTIVITY

Median FVIII activity from weeks 40 through 52 post-SPK-8016 infusion will be calculated by participant.

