3.3 Primary Endpoints

The primary endpoints include the following:

- For safety and tolerability:
 - Incidence of adverse events, including clinically significant abnormal laboratory values.
 - Occurrence of hepatic transaminase elevation requiring immunosuppression.
- For efficacy:
 - Peak and steady-state FVIII activity levels assessed by coagulation clotting assays. In this study, steady-state levels are based on FVIII:C measurements starting 12 weeks post vector administration and without the use of exogenous FVIII products since vector administration.
 - Number of bleeding events (spontaneous and traumatic) since vector administration.
 - Number of FVIII infusions since vector administration.

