Corticosteroid therapy may increase the transgene expression from the SPK-8016 expression cassette, similar to SPK-8011, as observed in both animal models and in our clinical observations using both early prophylactic and the reactive application of corticosteroids. In SPK-8011, this effect appears to occur in a dose-dependent fashion; in clinical observation the effect has appeared somewhat greater with initiation of daily oral corticosteroids in a prophylactic fashion in the early weeks after vector delivery when compared to reactive corticosteroids given at later time points. The Primary Endpoint for efficacy for this study is the FVIII activity at steady state,

which Spark does not interpret while any subject remains on corticosteroid treatment. Instead, expression level of steady-state FVIII:C as an efficacy endpoint is evaluated after daily oral corticosteroids or pulse steroids have been discontinued for at least 2 weeks. Note that if the concomitant use of steroids is to have an effect to artifactually increase the FVIII expression to a level greater than the eventual steady state expression (after discontinuation of steroids), this would not trigger an inappropriate escalation of the SPK-8016 dose (which would be a safety concern) but instead might result in an expansion of the present dose cohort or a delay in the decision to dose escalate until after the observation of steady state while off steroid therapy.

[REDACTED]

In consultation with the DMC, further dose exploration may be considered if effective immunomodulation has been demonstrated in any cohort and/or FVIII expression is less than 80% of normal 12 weeks following gene transfer in at least 2 participants.

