4.1.3.2 Other Immunomodulatory Considerations

Prolonged courses of high dose oral corticosteroids are undesirable and associated with adverse events. In the AASLD and the EASL guidelines for the treatment of autoimmune hepatitis, an alternative regimen of corticosteroids and steroid sparing agents, [REDACTED], is outlined for use in individuals who cannot tolerate high doses of prednisone or are experiencing difficulty tapering. A steroid-sparing agent administered concurrently with lower (compared to prednisone monotherapy) and tapering doses of prednisone may be utilized based on individual clinical circumstances. Both [REDACTED] have been utilized as steroid-sparing agents in the most recent iteration of this study, to good effect in both cases, and are described below.

[REDACTED]

The ultimate determination of steady state FVIII expression and determination of expression above a threshold FVIII:C activity value are interpreted by evaluating serial FVIII:C activity over multiple timepoints examined after discontinuation of corticosteroids and of steroid-sparing immune suppressive agents.

4.1.3.3 [REDACTED]

[REDACTED]

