Steady-state FVIII:C activity (central lab-recorded) from nominal week 12 through nominal week 52 following SPK-8016 administration will be summarized descriptively by SPK-8016 dose group. Using the same 4-week block construct already identified, an average value for each participant across all time points beginning with nominal week 12 will be computed, i.e., the average FVIII:C level across the individual participant's averages obtained across nominal weeks 12, 16, 20, 24, 28, 32, 36, 40, 44, 48 and 52. The proportion of participants who maintain a FVIII:C activity level $\geq 12\%$ across nominal weeks 12, 16, 20, 24, 28, 32, 36, 40, 44, 48 and 52 will also be obtained. Depending on the observed distribution, additional exploratory calculations may be performed to evaluate the proportion of participants with a FVIII:C activity level $\geq 12\%$ across, for example, at least 9 of these 11 timepoints to account for expected random variability. It is expected that corticosteroid therapy will increase the transgene expression from the SPK-8016 expression cassette; this effect is transient and dose-dependent so that as the corticosteroid is tapered and discontinued, the steady state FVIII expression from transduced hepatocytes becomes evident (not influenced by concurrent steroids). The assay of the FVIII activity that is measured while on corticosteroids (as assayed by one-stage and by chromogenic FVIII activity) appears not to be confounded, i.e., while on corticosteroids the observed hemostatic protection afforded by the transgene-derived FVIII is consistent with the measured FVIII activity and the increased measured level of FVIII is not an assay artifact. In contrast, [REDACTED] is expected not to influence levels of expression of the transgene product, as evaluated in pre-clinical animal studies (summarized in Section 2.2.4) and is expected not to have ongoing activity in circulation after week 12 (the timepoint after which the steady state FVIII:C activity is examined). For this reason, the treatment effect, i.e., determination of the ultimate steady state of FVIII:C activity resulting from the SPK-8016 dose, is not estimated while participants remain on corticosteroid therapy, and is evaluated after corticosteroids have been discontinued completely for at least 2-4 weeks. Additionally, the evaluation of the peak vector-derived FVIII:C activity may require careful interpretation if the participant is receiving corticosteroids at the time of peak activity, whereas [REDACTED] is not expected to have direct action on transgene expression and peak FVIII:C activity. One potential outcome at the conclusion of the study is that the peak FVIII:C activity may demonstrate a positive association with eventual steady state FVIII:C activity for participants who are not receiving reactive corticosteroids at time of peak activity (in Cohort 1 and Cohort 2) but may fail to demonstrate an association for participants whose peak FVIII:C activity occurs during concurrent treatment with corticosteroids. This potential confounding effect will be considered in the descriptive statistical review.

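### The SAP's week 40–52 FVIII median drops the protocol's steady-state conditions without explanation, and for three of the first four participants the window falls largely on prednisone if their courses were uninterrupted

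*SAP*

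**What the plan says.** SAP 1.1.1 keeps FVIII expression within a primary objective. SAP 1.2.2 lists two FVIII activity endpoints, peak and a late median. SAP 3.3.2 defines the median in one sentence: "Median FVIII activity from weeks 40 through 52 post-SPK-8016 infusion will be calculated by participant". No treatment condition is attached, and none is supplied elsewhere. SAP 3.3 and 3.4.3 list FVIII values by participant, SAP 3.4.1 lists immunosuppressant use separately under safety, and the censoring rules in SAP 3.2.1 and 3.2.2 apply only to bleeding and infusion rates.

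The protocol treats the late level differently:

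- Section 4.1.1.1 names the endpoint: "The Primary Endpoint for efficacy for this study is the FVIII activity at steady state". The same section then limits how that level may be read: "which Spark does not interpret while any subject remains on corticosteroid treatment". It also sets a washout, under which the level is to be "evaluated after daily oral corticosteroids or pulse steroids have been discontinued for at least 2 weeks".
- Section 10.5.3: the steady-state level "is not estimated while participants remain on corticosteroid therapy, and is evaluated after corticosteroids have been discontinued completely for at least 2-4 weeks".
- Section 4.1.3.2: it is interpreted from serial values "examined after discontinuation of corticosteroids and of steroid-sparing immune suppressive agents".
- Section 3.3: it rests on measurements "starting 12 weeks post vector administration and without the use of exogenous FVIII products since vector administration".

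The protocol is not fully consistent with itself. The calculation in section 10.5.3 says "an average value for each participant across all time points beginning with nominal week 12 will be computed", and that recipe has no step that removes on-steroid values. The washout is also stated in two ways, at least 2 weeks and at least 2–4 weeks.

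**The concern.** The SAP never calls its median steady state. It is nevertheless the only summary of sustained expression offered for a primary objective, and it sits where the protocol's steady-state endpoint would be. Followed as written, it can summarise values that the protocol says are not to be interpreted. Protocol 10.5.3 expects corticosteroids to raise transgene expression for a time, so an on-treatment median could be read as durable expression. The study has no hypothesis test and few participants, so each participant's value is effectively the result and its definition matters.

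**Working it through.** The study is descriptive (Protocol 10.1, SAP 1.3.1), so there is no planned figure to reproduce. The check is timeline arithmetic.

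Inputs:

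- SAP window: weeks 40 to 52, a length of 12 weeks (SAP 3.3.2).
- Prednisone start: about week 3 to 6 (Protocol 1 and 4.1.3).
- Course length: 43 to 48 weeks in three of the first four participants (Protocol 1).
- Washout: 2 weeks (Protocol 4.1.1.1) or 2–4 weeks (Protocol 10.5.3), so 2 and 4 are used.
- Routine FVIII visits in the window: weeks 40, 46 and 52, each ±2 weeks (Protocol 6.8.2).
- Assumption: each course was continuous. Starts and courses are not paired in the documents, so the range combines the extremes.

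Stop week = start + course, which runs from 3 + 43 = 46 to 6 + 48 = 54.

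Ineligible share of the window = (min(stop + washout, 52) − 40) / 12:

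| Rule | Stop at week 46 | Stop at week 54 |
|---|---|---|
| On prednisone | (46 − 40)/12 = 50% | 12/12 = 100% |
| With 2-week washout | (48 − 40)/12 = 67% | 100% |
| With 4-week washout | (50 − 40)/12 = 83% | 100% |

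**Routine visits.** The first eligible week is 48 to 56 (2-week washout) or 50 to 58 (4-week washout), so at most the week 52 visit qualifies. There are 4 starts × 6 course lengths = 24 whole-week combinations. No routine visit is eligible in 10 of them with a 2-week washout (stop at week 51 or later: 4 + 3 + 2 + 1), and in 18 with a 4-week washout (stop at week 49 or later: 4 + 4 + 4 + 3 + 2 + 1). In all 24, at least two of the three nominal visits fall on prednisone or inside the 2-week washout. These are counts of combinations, not probabilities.

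**Weekly visits.** Protocol 6.8.1 and 6.8.2 call for weekly FVIII sampling during immunomodulation. SAP 3.7.1 defaults to nominal visits, and SAP 3.3.2 does not say whether the extra values enter.

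- With a value at each of the 13 weeks from 40 to 52, a week-46 stop leaves weeks 48–52 (5 values) or weeks 50–52 (3 values), falling to 0 for later stops.
- If weekly sampling ran only while on prednisone (an assumption), a week-46 stop gives weeks 40–46 plus week 52, so 1 of 8 values is eligible. A week-54 stop gives 0 of 13.

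**Not computable.** No course data are given for Cohorts 1 and 2. Two of the three participants also had a steroid-sparing regimen, but the documents give no usable dates. No figures describe exogenous FVIII use around these samples. No multiplier for the steroid effect is given, so the size of any bias cannot be derived.

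**The case against.** The strongest reply is that nothing is hidden. FVIII values are listed by participant and visit, immunosuppressant use is listed by participant, and the median is filed under pharmacokinetics without being called steady state. The late window is also less exposed than the protocol's own averaging recipe. That recipe has 11 four-week blocks covering weeks 9–52, or 44 weeks. A week-46 stop puts 9 blocks wholly on prednisone (38/44 = 86% of the time), and a stop at week 52 or later puts all 11 there. The course data are approximate as well. A total course given partly to treat recurrences may contain gaps, and a gap inside weeks 40–52 would break the 50% floor and the eligible-value counts.

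All of this stands as fact. It does not supply the missing rule. A reader can cross-check listings by hand, but the summary remains unconditioned. The protocol's prose also states the off-steroid condition even though its formula omits it.

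Three stronger readings are tempting and are not supported:

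- That the median is the only late FVIII result. It is the only late summary; by-visit values are listed.
- That the median must be steroid-inflated. Protocol 10.5.3 calls the effect transient and dose-dependent, with the underlying level emerging as the steroid is tapered and stopped. It does not say that late-taper or washout values run high.
- That steroid-sparing agents or exogenous FVIII have been shown to distort the median. Those parts rest on omission alone.

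**Conclusion.** The concern holds as an endpoint mismatch. The SAP replaces a conditioned primary endpoint with an unconditioned late median and gives no reason. For three of the first four participants, and only if their courses were uninterrupted, half to all of the window is on prednisone. Under the protocol's own washout, two-thirds to all of it (2 weeks) or five-sixths to all of it (4 weeks) is ineligible. The expected direction of bias is upward. The case for correction rests on the mismatch, not on a demonstrated distortion of the reported levels.

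**What to change.** In SAP 3.3.2:

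- Add a per-participant steady-state FVIII from central one-stage values at week 12 or later, using only values taken off corticosteroids (daily or pulse) and off steroid-sparing agents.
- Reconcile Protocol 4.1.1.1 and 10.5.3 into one stated analysis washout, with the other as a sensitivity analysis. Report how many participants are not estimable.
- Keep the all-values week 40–52 median as supportive, labelled as not protocol steady state. Flag each value for steroid, steroid-sparing and exogenous FVIII use, and state whether weekly immunomodulation visits enter.
- Reconcile the no-exogenous-FVIII condition in Protocol 3.3 with the on-demand use that Protocol 7.9.2 permits, and report how many participants meet the condition as written.

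The cost is SAP wording and a merge of FVIII, concomitant-medication and infusion-log data already collected. The downside is fewer eligible values, some participants not estimable, and possibly lower reported levels. For some, the first eligible week falls after week 52, and later visits exist only if the participant stayed on because the long-term follow-up study was not yet enrolling.
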